#### 10.5.2.4 ECOG Performance Status

ECOG performance status (PS) scale as described in Table 7-3 will be used to assess physical health of patients. An analysis of the time to definitive deterioration of the ECOG PS by at least one category of the score from baseline will be performed. A deterioration is considered definitive if no improvements in the ECOG PS are observed at subsequent measurement times during the treatment period following the time point at which the deterioration is observed.

Death will be considered as worsening of the ECOG PS if it occurs close to the last available assessment, where "close" is defined as being within twice the planned period between two assessments. Patients who die after more than twice the planned period between two assessments will be censored at the date of their last assessment before the cut-off.

Patients receiving any further anti-neoplastic therapy prior to definitive worsening will be censored at their date of last assessment prior to the start of therapy. Patients that have not worsened at the data cut-off point will be censored at the date of last assessment prior to the cutoff

The Kaplan-Meier estimation method will be used to assess the distribution of time to definitive worsening in the ECOG PS score, stratified by treatment. The estimated treatment-specific median times to definitive worsening will be presented along with 90% confidence intervals.

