Time windows will be defined for summaries of ECOG data. If more than one assessment is available in the same time window, the assessment closest to the planned date will be considered. If two assessments are obtained with the same time difference compared to the scheduled visit day, the assessment with the worst value will be considered. Data obtained at the end of treatment will be classified as other assessment in the corresponding time window. Note that only data collected under treatment (i.e. while the patient is treated and up to 7 days after last dose intake) will be included in the time to deterioration analysis. Post-treatment data will be summarized separately. The end of treatment assessment will be included if collected within 7 days of the last dose intake.

Time Window	Planned visit timing	Time Window Definition
Baseline	On or before Study Day 1	<= Study Day 1
Week 6	Study Day 43	Study Days 22-63

Week 12	Study Day 85	Study Days 64-105
Week 18	Study Day 127	Study Days 106-147
Every 6 weeks thereafter, Week $y=18+6*k$ (with $k=1,2 \dots$)	Study Day $(18+6*k)*7+1$	Study Days $(18+6*k)*7-20$ to $(18+6*k)*7+21$ Note: EOT data visit are included if obtained within 7 days of last non-0 dose intake.
Study Day 1 = randomization date		

Frequencies of patients with ECOG PS values of 0, 1 or ≥ 2 will be used to summarize the ECOG PS data at each time window. .

An analysis of the time to definitive deterioration of the ECOG PS by at least one category of the score from baseline will be performed. A deterioration will be considered definitive if no improvements in the ECOG PS are observed at subsequent measurement times during the treatment period following the time point at which the deterioration is observed. (Example 1: if the score is 1 at baseline and then 1, 2, 1, 2, 3 at study days 28, 57, 83, 115, 150, respectively, then the time to definitive worsening is 115 days. Example 2: if the score is 1 at baseline and then 1, 1, 2 at study days 28, 57, 83, respectively, with no assessment of the ECOG performance status after day 83, then the time to definitive worsening is 83 days.)

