Definitive 10% (5- or 10-point) deterioration is defined as a decrease in score by at least 10% (5 or 10 points) compared to baseline, with no later increase above this threshold observed during the course of the study. Baseline is defined as the latest available assessment made on or before the date of randomization when patient can still deteriorate. Time to definitive deterioration is the number of days between the date of randomization and the date of the assessment at which definitive deterioration is seen.

Death will be considered as deterioration of symptoms/QoL if it occurs close to the last available assessment where “close” is defined as twice the planned period between two assessments. This avoids overestimating the time to definitive worsening in patients dying after an irregular assessment scheme. Patients who die after more than twice the planned

period between two assessments since the last assessment will be censored at the date of their last available questionnaire.

Patients receiving any further anti-neoplastic therapy before definitive worsening will be censored at the date of their last assessment before starting this therapy. Patients that have not worsened as of the cut-off date for the analysis will be censored at the date of their last assessment (questionnaire) before the cut-off.

Treatment satisfaction questionnaire for medication (TSQM)

Patients' self-reported satisfaction or dissatisfaction with the study treatment will be measured using the Treatment Satisfaction Questionnaire for Medication (TSQM) version 1.4. TSQM is planned to be administered at week 3, 6, 12, and the end-of-treatment (EOT) visit. The questionnaire will be administered in the patients' local language.

TSQM items will be divided into four scales: side effects, effectiveness, convenience, and global satisfaction. Raw TSQM data will be scored according to the scoring manual. Only scale scores with not more than one missing item will be computed.

The following time-based intervals will be used to group TSQM data over time. Day x is defined as date of TSQM administration – randomization date + 1. If more than one assessment is available in the same time window, the assessment closest to the planned date will be considered. If two assessments are obtained with the same time difference compared to the scheduled visit day, the assessment obtained prior to scheduled visit day will be considered.

Time window	Planned visit timing	Time Window Definition

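### The ECOG definition does not say what level of later improvement undoes a deterioration; read literally, a partial recovery that is still worse than baseline postpones the event to the day of recovery

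*SAP*

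**What the plan says.** SAP 3.8.2 sets the endpoint as "time to definitive deterioration of the ECOG PS by at least one category of the score from baseline". It then tests permanence: "A deterioration will be considered definitive if no improvements in the ECOG PS are observed at subsequent measurement times during the treatment period". Protocol 10.5.2.4 agrees: "A deterioration is considered definitive if no improvements in the ECOG PS are observed at subsequent measurement times during the treatment period". Neither text says whether an improvement must reach baseline, must cross the one-category threshold, or may be any step in the better direction.

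Two worked examples follow in the SAP, both from baseline 1. In the first the only improvement is a full return to baseline; in the second there is none.

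For the QLQ-C30 scales, the same SAP section cancels a deterioration only by reference to the size of change that defines it: "with no later increase above this threshold observed during the course of the study". Protocol 10.5.2.5 does likewise.

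The ECOG endpoint uses data collected on treatment and up to 7 days after the last dose. It is reported as Kaplan-Meier medians by arm and, in the SAP, as two stratified Cox hazard ratios with 90% intervals.

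**The concern.** The event is defined against baseline, but permanence is tested against improvement with no stated reference. For a patient who drops two categories and regains one, the two parts can conflict. She is worse than baseline by the required amount at every visit, yet the literal words cancel each visit before the partial recovery and place the event on the day she got better. A patient who drops one category and stays there is dated at the first visit. The patient with the deeper decline is therefore credited with the longer time to deterioration, which is the wrong order for this endpoint.

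Two programmers could follow the text and both examples and still derive different dates for the same patient. What is at stake is the dating of some events in one secondary endpoint.

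**Working it through.** Inputs. The threshold is a score of at least baseline + 1 (SAP 3.8.2). Planned assessment days are 43, 85 and 127, then (18 + 6k) × 7 + 1, which gives 24 × 7 + 1 = 169 and 30 × 7 + 1 = 211 (SAP 3.8.2, ECOG time windows). Protocol 5.2 prints the entry criterion as ECOG PS below 2, so baseline 0 and 1 both occur.

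Under each reading, the event is the first visit with a score of at least baseline + 1 that is not cancelled later. Three readings were compared:

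- A (literal): any later visit-to-visit improvement cancels.
- B (relative): a later score better than the score on that day cancels.
- C (threshold, as for QoL): only a later score better than baseline + 1 cancels.

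The SAP's own figures come first. The first worked example has this sequence: "if the score is 1 at baseline and then 1, 2, 1, 2, 3 at study days 28, 57, 83, 115, 150". The SAP's answer for it is 115 days. For the second, shown in the second row of the table, the answer is 83 days. All three readings reproduce both answers, so the examples do not separate them.

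| Baseline | Scores | Days | A | B | C |
|---|---|---|---|---|---|
| 1 | 1, 2, 1, 2, 3 (Example 1) | 28, 57, 83, 115, 150 | 115 | 115 | 115 |
| 1 | 1, 1, 2 (Example 2) | 28, 57, 83 | 83 | 83 | 83 |
| 0 | 1, 1, 1, 1, 1 | 43 to 211 | 43 | 43 | 43 |
| 0 | 2, 2, 2, 2, 1 | 43 to 211 | 211 | 211 | 43 |
| 0 | 2, 2, 2, 1 | 43 to 169 | 169 | 169 | 43 |
| 0 | 2, 1, 1, 1, 1 | 43 to 211 | 85 | 85 | 43 |
| 0 | 1, 2, 2, 1 | 43 to 169 | 169 | 43 | 43 |
| 1 | 3, 3, 3, 2 | 43 to 169 | 169 | 169 | 43 |
| 1 | 2, 2, 2, 1 | 43 to 169 | none | none | none |

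Delays of A relative to C: 211 − 43 = 168 days, 169 − 43 = 126 days, and 85 − 43 = 42 days (one visit).

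Three things follow.

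- A visit that survives A also survives C: if scores never improve after it, they stay at or above baseline + 1. The literal date is therefore the same as the threshold date or later, never earlier.
- The readings separate only when the score reaches baseline + 2 or more and then partly recovers.
- If the patient passes through the intermediate category on the way down (scores 1, 2, 2, 1), only A delays the event. If she skips it, A and B both do.

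**The case against.** The best reply is that the sentence is unclear rather than wrong. The SAP first fixes the deterioration as one category from baseline and then asks whether that deterioration lasts, so no improvement can fairly mean no recovery from it. That is the threshold reading; it fits both examples, and the only improvement illustrated is a full return to baseline. This stands: a reader might infer that the plan definitely cancels a deterioration after any improvement, but the text does not compel that. It equally does not exclude it, and no other section settles the matter.

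One could also say that ECOG is a coarse ordinal scale, so the QoL wording need not carry over, and that a stricter notion of definitive is conceivable. That is fair as a matter of choice. It does not remove the ordering problem when the stricter rule dates the worse patient later.

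The 168-day example is an extreme case. It needs four consecutive visits at PS 2 from baseline 0, then a recovery at day 211 while still in the on-treatment window and before any new anti-neoplastic therapy, which would censor. The planning medians for PFS of 7, 4 and 6 months are about 213, 122 and 183 days (at 30.4375 days per month), so day 211 is at or beyond the assumed median in every arm. The 42-day shift needs much less follow-up.

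A reader might also infer that the rule favours a regimen whose toxicity is deep but partly reversible. Protocol 2.1 says that the safety profiles of chemotherapy and of everolimus with endocrine treatment differ, but neither document gives depth or recovery of ECOG PS by arm. A between-arm bias, and its direction, are not supported.

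**Conclusion.** The definition needs correcting at low priority. As worded it permits a derivation in which a patient who was never in better condition than a comparator is given a later deterioration date, by 42 to 168 days in the five-visit examples. The text also permits a threshold derivation without this fault, and the worked examples cannot tell the two apart.

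The effect is confined to patients who worsen by two or more categories and then partly recover on treatment, mainly those who skip the intermediate category. A change from PS 2 to PS 1 is a partial recovery only from baseline 0; from baseline 1 it is a full return, and no event results under any reading. The number of such patients is not given and is probably small. The size of any shift in the medians or hazard ratios cannot be computed from the documents. PFS, OS and the precision calculation are unaffected.

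**What to change.** Replace the sentence in SAP 3.8.2, and its counterpart in Protocol 10.5.2.4, with a rule of this form: *a deterioration is definitive if no later on-treatment ECOG PS is less than one category worse than baseline.* Add a third example with a partial recovery: baseline 0, scores 2, 2, 1, event at the first 2. Examples 1 and 2 keep their answers of 115 and 83 days.

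The SAP already carries an addendum dated after database lock, so the change should be recorded as a clarification that states which rule was programmed. If it was the literal one, report the threshold version alongside it and document the change.

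The cost is one sentence, one example and about one line of code, with no new data. The downside is that some event dates move earlier.

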#### Quality of life questionnaire (QLQ)

The EORTC QLQ-C30 questionnaire along with the breast module (BR23) will be used to collect patients' quality of life (QoL) data. Raw QoL data will be scored according to the EORTC scoring manual. The global health status/QoL scale score is identified as the primary QoL variable of interest. Physical functioning, emotional functioning and social functioning scale scores are identified as secondary QoL variables of interest.

The number of patients providing QoL data and the number of patients missing/expected to have QoL assessments will be summarized by each treatment group for scheduled assessment time points.

Descriptive statistics (count, mean, median, standard deviation, first and third quartile) will be used to summarize individual item and multi-item scale scores at each scheduled assessment time. Patients will be included if they completed at least one questionnaire item. Additionally, change from baseline in the scale scores at the time of each assessment will be summarized.

Time to definitive 10% deterioration in the global health status / QoL, and in each of the three secondary scales, will be examined for the three treatment arms. In addition, time to definitive

5-point deterioration in the global health status / QoL score will be explored for each treatment arm. The assessed distributions will be presented descriptively using Kaplan-Meier curves. Summary statistics based on Kaplan-Meier distributions will be presented, including the estimated median time to definitive 10% (5-point) deterioration and the probability of not experiencing definitive 10% (5-point) deterioration by 12 and 24 weeks. Both point estimates and 90% confidence intervals will be presented.

Definitive 10% (5-point) deterioration is defined as a decrease in score by at least 10% (5-points) compared to baseline, with no later increase above this threshold observed during the course of the study. A single-item measure reporting a decrease of at least 10% (5-point) is considered definitive only if it is the last one available for the patient. Baseline is defined as the latest available assessment made on or before the date of randomization. Time to definitive deterioration is the number of days between the date of randomization and the date of the assessment at which definitive deterioration is seen.

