### 14.1.34 Calculation of 'time to event' variables

Time to event = end date - start date + 1 (in days)

When no post-baseline tumor assessments are available, the date of randomization/start of treatment will be used as end date (duration = 1 day) when time is to be censored at last tumor assessment, i.e. time to event variables can never be negative.

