2.1.6 Study day

The study day for *safety assessments* (e.g., adverse event onset, laboratory abnormality occurrence, vital sign measurement, dose interruption, etc.) will be calculated as the difference between the date of the assessment and the start of study treatment plus 1. (*Note: except in the case when the assessment is before start of study treatment in which case study day is calculated as the difference between the date of the assessment and the start of study treatment. In this particular case, the study day displayed on the listing will be negative.*)

The study day for *all other, i.e., non-safety assessments* (tumor assessment, death, disease progression, tumor response, ECOG performance status, QoL assessment) will be calculated as the difference between the date of the event and the randomization date plus 1. In other words, all efficacy time-to-event variables (e.g., progression-free survival, overall survival, time to response) will be calculated from date of randomization. (Example: if randomization date is 02JAN2007, start of study drug is on 05JAN2007, and the date of death is 09JAN2007, then the study day when death occurred is 8.)

The study day will be displayed in data listings.

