The EORTC QLQ-C30 questionnaire along with the breast module (BR23) will be used to collect patients' quality of life (QoL) data. Raw QoL data will be scored according to the EORTC scoring manual. If at least half of the items comprising the scale have been answered, the score for this scale will be calculated. For single item scales with missing responses and scales where less than half of the items have been answered, the score for these scales will be set to missing. The global health status/QoL scale score is identified as the primary QoL variable of interest. Physical functioning, emotional functioning and social functioning scale scores in QLQ-C30, and functional and symptom scale scores in BR23 are identified as secondary QoL variables of interest.

QLQ-C30 and BR23 will be assessed and recorded at baseline, on Treatment Day 1, at week 6 and every 6 weeks thereafter as well as at discontinuation from the study treatment (within one week after discontinuation). If patients discontinue study treatment for any reason other than progression, lost to follow-up or consent withdrawal, the QLQ-C30 and BR23 performance status and will continue to be performed every 6 weeks until progression, lost to follow-up, consent withdrawal or investigator decision in patient best interest.

Time windows will be defined for descriptive summaries of PRO data. If more than one assessment is available in the same time window, the assessment closest to the planned date will be considered. If two assessments are obtained with the same time difference compared to the scheduled visit day, the assessment obtained prior to scheduled visit day will be considered. Data obtained at the end of treatment will be classified as other assessment in the corresponding time window. Note that only data collected under treatment (i.e. while the patient is treated and up to 7 days after last dose intake) will be included in the time to deterioration analysis. Post-treatment data will be summarized separately. The end of treatment assessment will be included if collected within 7 days of the last dose intake.

Time Window	Planned visit timing	Time Window Definition
Baseline	On or before Study Day 1	<= Study Day 1
Week 6	Study Day 43	Study Days 22-63
Week 12	Study Day 85	Study Days 64-105
Week 18	Study Day 127	Study Days 106-147

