Every 6 weeks thereafter, Week $y=18+6*k$ (with $k=1,2 \dots$)	Study Day $(18+6*k)*7+1$	Study Days $(18+6*k)*7-20$ to $(18+6*k)*7+21$ Note: EOT data visit are included if obtained within 7 days of last non-0 dose intake.

Study Day 1 = randomization date

The number of patients filling QoL data and the number of patients missing/expected to have QoL assessments will be summarized by each treatment group for scheduled assessment time points. Furthermore, the amount and the pattern of missing data will be explored by treatment group and over time. The following categories will be used to describe whether the questionnaire was completed at a specific time point:

- yes, fully completed
- yes, partially completed
- no, patient (or subject) missed scheduled assessment visit
- no, patient refused due to poor health
- no, patient (or subject) refused (unrelated to health)- no, study staff felt patient was too ill
- no, questionnaire not available
- no, institutional error
- no, other

Other exploratory analyses may be performed to better understand the missingness pattern for QoL data.

Descriptive statistics (count, mean, median, standard deviation, first and third quartile) will be used to summarize domains at each scheduled assessment time. Patients will be included if they completed at least one questionnaire item. Additionally, change from baseline in the scale scores at the time of each assessment will be summarized. Patients with an evaluable baseline score and at least one evaluable post-baseline score during the treatment period will be included in the change from baseline analysis.

Time to definitive 10% deterioration in the global health status / QoL score, and in each of the three secondary scales, will be examined for the three treatment arms. In addition, time to definitive 5-point and 10-point deterioration in the global health status / QoL score will be explored for each treatment arm. The assessed distributions will be presented descriptively using Kaplan-Meier curves. Summary statistics based on Kaplan-Meier distributions will be presented, including the estimated median time to definitive 10% (5-, 10-point) deterioration and the probability of not experiencing definitive 10% (5-, 10-point) deterioration by 12 and 24 weeks. Both point estimates and 90% confidence intervals will be presented.

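### Do two day-count rules leave the 12- and 24-week quality-of-life probabilities unsettled?

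*SAP*

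**What the plan says.** Protocol 10.5.2.5 asks for the probability of not "experiencing definitive 10% (5-point) deterioration by 12 and 24 weeks". SAP 3.8.2 repeats this with a 10-point version added: "the probability of not experiencing definitive 10% (5-, 10-point) deterioration by 12 and 24 weeks". The SAP time-window table plans the week-12 visit on Study Day 85. Its formula for later visits gives Study Day 169 for week 24. Study Day 1 is the randomization date.

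Two day counts appear:

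- **Elapsed days.** The QoL paragraph of SAP 3.8.2 says "Time to definitive deterioration is the number of days between the date of randomization and the date of the assessment" at which the deterioration is seen. Protocol 10.5.2.5 has the same definition.
- **Difference plus 1.** SAP 2.1.6 lists QoL among the non-safety assessments whose study day is counted this way ("QoL assessment) will be calculated as the difference between the date of the event and the randomization date plus 1"). Protocol 14.1.34 gives the general formula "Time to event = end date - start date + 1 (in days". The ECOG worked example in SAP 3.8.2 follows it: for a worsening at study day 115, "then the time to definitive worsening is 115 days".

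Neither document says which count takes precedence for QoL.

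**The concern.** A Kaplan-Meier estimate at time t includes events at t, so a one-day shift matters only when many events fall on t itself. Here they may, because QoL is assessed every 6 weeks and the landmark coincides with the planned visit. If times are computed with plus 1 and the curve is read at 84 days, a deterioration found punctually at week 12 is left out. With elapsed days it is counted. Two programmers working from the same documents and data could print different 12- and 24-week probabilities.

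Visits may also be up to 7 days late (protocol Table 7-1), and a late visit falls past the landmark under either count. At stake is how far these printed figures can be relied on, and whether they look more favourable than the visit schedule implies.

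**Working it through.** **The plan's own figures.** Planned study day = 7 × week + 1, which gives 43, 85, 127 and 169 for weeks 6, 12, 18 and 24, matching the SAP table. The SAP 2.1.6 example (randomized 02JAN2007, death 09JAN2007) gives 7 + 1 = 8, as stated.

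**On-schedule visits under each rule.**

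| Visit | Landmark | Elapsed days | Plus 1 |
|---|---|---|---|
| Week 12, Study Day 85 | 84 | 84, counts | 85, does not count |
| Week 24, Study Day 169 | 168 | 168, counts | 169, does not count |

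The last column needs plus-1 times to be paired with a cut at 84 or 168. Neither document states a cut in days. A programmer who uses plus 1 and reads the curve at Study Day 85, which the SAP labels week 12, gets the elapsed-day answer.

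**The protocol's own visit day.** Table 7-1 puts the 12-week visit on treatment day 84, and protocol 7.1.1.4 asks for the first dose on the day of randomization. With same-day dosing, a day-84 visit has time 83 or 84 and counts under both rules. This weakens if dosing starts later, since protocol 7.1.2 allows up to 7 days.

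**How many visits change sides.** For a visit planned on Study Day 85 with a ±7-day window there are 15 possible days. Elapsed times run from 77 to 91, and 8 of the 15 are at or below 84. Plus-1 times run from 78 to 92, and 7 of the 15 are. Only the exact planned day changes sides.

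**Size.** The documents give neither visit punctuality nor a QoL median, so both are assumptions. Take exponential times with median m months, S(d) = exp(−ln 2 × d / (30.4375 × m)), with events found only at scheduled visits.

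- m = 6: S(42) = 85.3% and S(84) = 72.7%, a week-12 step of 12.56 points. S(126) = 62.0% and S(168) = 52.9%, a week-24 step of 9.13 points.
- Visits uniform over the window: 12.56 / 15 = 0.84 points at week 12 and 9.13 / 15 = 0.61 at week 24.
- m = 4: the week-12 step is 16.74 points, so 16.74 / 15 = 1.12. m = 12: the step is 7.07 points, so 7.07 / 15 = 0.47.
- Every visit on the planned day (m = 6): the full step, 12.6 points at week 12 and 9.1 at week 24.

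For scale, with 100 patients per arm and no censoring, the 90% confidence half-width at 72.7% is 1.645 × √(0.727 × 0.273 / 100) = 7.3 points. Events away from the visit grid make the steps smaller. These include deaths and end-of-treatment questionnaires ("The end of treatment assessment will be included if collected within 7 days of the last dose intake").

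**The late-visit part.** With uniform visits and m = 6, late visits lift the week-12 reading above the all-visits-counted value by 7/15 × 12.56 = 5.86 points under elapsed days and 8/15 × 12.56 = 6.70 under plus 1. The difference, 0.84, is all that the day-count rule contributes. The 5.86 remains whichever rule is chosen.

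**The case for a change.** The strongest case for acting is that the plus-1 rule is not confined to listings. SAP 2.1.6 names QoL and carries its rule over to efficacy time-to-event variables. Protocol 14.1.33 presents its rules as the ones for programming efficacy results. SAP 4.2 groups QoL deterioration with PFS, OS and ECOG under one methodology, and the ECOG endpoint in the same SAP section visibly uses plus 1. One sentence would remove the doubt, and a supplementary reading at days 92 and 176 would also take in every in-window late visit.

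What stands is that the wording is inconsistent and no precedence is stated. A line in the programming specification would be sensible housekeeping.

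The rest does not carry a change. An endpoint-specific definition, repeated identically in protocol and SAP, is ordinarily read as governing over a general study-day convention or a generic solid-tumour appendix. The late-visit gap is not an error either: the event is defined at the assessment date, and reading the curve at nominal time is standard and correct for that definition. Days 92 and 176 are a matter of preference. The SAP's own windows close at Study Days 105 and 189, and the later cut also picks up off-grid events: S(84) − S(92) = 2.2 points at week 12 and S(168) − S(176) = 1.6 at week 24 if all events were off-grid and m = 6. The database is already locked, so this would add a post-lock estimate to a descriptive table whose full curve is shown anyway.

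**Conclusion.** This is a gap in detail that analysts fill sensibly, and no change to the plan is needed. Following the QoL definition as written, with the landmarks at 84 and 168 elapsed days (equivalently Study Days 85 and 169), counts on-schedule visits and gives a sound result.

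If the other count were programmed and cut at 84 and 168, the expected effect is about 0.8 points at week 12 and 0.6 at week 24, assuming a 6-month median and visits spread evenly over the window. At week 12 it runs from about 0.5 to 1.1 points for medians of 12 to 4 months. It reaches 12.6 and 9.1 points only if every visit falls exactly on the SAP's planned day and no event falls off the grid.

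Plus 1 shifts every patient's QoL time by the same single day in all arms, so medians move by about a day and no between-arm bias is shown. The estimates are descriptive and secondary, and the primary PFS hazard ratio is unaffected.
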